3.6 Post-operative adjuvant radiotherapy or radiochemotherapy

If the postoperative pathology report suggests the presence of risk factors associated with recurrence (high-risk factors or intermediate risk factors), postoperative adjuvant therapy is required if necessary.

(1) High-risk factors: positive parametrium, positive incisional margins, and positive pelvic lymph nodes.

Positive parametrium: external pelvic beam radiation therapy (EBRT) + cisplatin concurrent chemotherapy. Cisplatin (DDP) 40 mg/m²/w (week, w), or carboplatin if cisplatin is not tolerated (AUC=2). (If positive for parametrial tissue, local push of 5-10 Gy may be appropriate).

Positive vaginal incisional margins: external pelvic radiation therapy (EBRT) + cisplatin concurrent chemotherapy + vaginal backloading radiotherapy, with cisplatin (DDP) 40 mg/m²/w, or carboplatin (AUC=2) if cisplatin is intolerant.

Positive pelvic lymph nodes: one course of systemic chemotherapy + external pelvic radiation radiotherapy (EBRT) \pm extended field radiotherapy to the abdominal aorta + concurrent chemotherapy with cisplatin (40 mg/m²/w) + 3-6 courses of adjuvant systemic chemotherapy after radiotherapy (paclitaxel + cisplatin or carboplatin preferred

for large intravenous chemotherapy regimens, can use both domestic or imported). If the pathology confirms positive abdominal aorta or positive common iliac lymph nodes, irradiation of para-aortic extended field will be performed; when the pelvic lymph nodes are positive and the pathology result of abdominal aortalymph nodes clearance is negative (if only abdominal main biopsy without clearance, positive irradiation will be performed, negative is equivalent to no clearance), no extended field irradiation will be performed; if the lymph nodes in the pelvic lymph nodes are positive and the lymph nodes in the para-aortic lymph nodes are not cleared, but the image is suspected of metastasis in the para-aortic lymph nodes (full lymph nodes, length to diameter ratio close to 1), it is recommended to extend field irradiation.

(2) Intermediate risk factors (tumor size, interstitial infiltration, positive lymphovascular space), squamous carcinoma according to "Sedlis criteria": external pelvic radiation therapy (EBRT) + cisplatin concurrent chemotherapy, cisplatin (DDP) 40mg/m²/w.

(3) Adenocarcinoma and adenosquamous carcinoma are treated according to intermediate risk factors, following the four-factor approach (i.e. adenocarcinoma or adenosquamous carcinoma with positive lymphovascular space, tumor ≥ 3 cm, and infiltration of the outer 1/3 of the cervical canal should be treated with concurrent radiotherapy). External pelvic radiation therapy (EBRT) + cisplatin concurrent chemotherapy with cisplatin (DDP) 40 mg/m²/w, or carboplatin (AUC=2) if cisplatin is not tolerated.

(4) Positive proximal margin (negative margin ≤ 0.5 cm), treatment as positive vaginal margin, external pelvic irradiation therapy + cisplatin concurrent chemotherapy + brachytherapy.

The EBRT implementation:

(1) Recommend to start at 4 weeks postoperatively and no later than 8 weeks.
Prescribed dosage: squamous carcinoma, 45 Gy; adenocarcinoma, 50.4 Gy; conventional segmentation 1.8 Gy per session, once daily, Monday through Friday each week. Large unresectable metastatic lymph nodes are given a simultaneous additional push (SIB 2.1-2.2Gy) or sequential additional dose of 10-15Gy.

(2) Scope of irradiation: pelvic radiation field \pm extended abdominal aortic field \pm brachytherapy.

(3) Pelvic radiation field: at least 3-4 centimeters below the vaginal dissection, parametrial tissue and adjacent lymph node drainage areas (common iliac, internal and external iliac lymph nodes, closed foramen, presacral) must be included.

(4) Para-aortic extension field: the upper border reaches the level of the left renal vein, the left side reaches the inner edge of the psoas major muscle and the right side 3-5 millimeters around the inferior vena cava.

(5) Intensity-modulated radiation therapy (IMRT) or volumetric-modulated

arcadiotherapy (VAMT) is recommended for EBRT with weekly cone beam CT (CBCT) once a week.

The Implementation of retrovaginalradiotherapy

(1) Retrovaginal radiotherapy is started after the completion of external pelvic irradiation, twice per week. (It is recommended that the total duration of external irradiation radiotherapy + retrovaginal radiotherapy treatment does not exceed 56 days).

(2) Recommend 3-D rear-loading technique: CT or MRI localization, using columnar and ovoid applicators with ^{192}Ir -source or ^{60}Co , for high-dose-rate rear-loading radiotherapy.

(3) High-risk clinical target volume (HR-CTV): including the area 5 millimeters outside the vaginal mucosa and 1 centimeter above the vaginal stump.

(4) More than 90% of the volume of HR-CTV per session is included in the prescribed dose range (6 Gy \times 3 sessions); for two-dimensional rear-loading radiotherapy plans, the prescribed dose point is 5 millimeters below the vaginal mucosa.

(5) The sum of external rectal irradiation and 2 Gy equivalent total dose (EQD2) of postoperative radiotherapy (2cc) is less than 65~75 Gy; sigmoid colon is less than 70-75 Gy, and bladder 2cc is less than 80~90 Gy.

The implementation of CCRT.

CCRT is given weekly cisplatin (DDP) intravenous chemotherapyduring EBRT. Cisplatin (DDP) 40 mg/m²/w is recommended for the first 3 days of the first week of radiotherapy initiation, with an expected 5 cycles.

Note: SEDLIS criteria

LVSI	Depth of interstitial invasion	Tumor size(cm) (determined by clinical gynecological examination)
+	Deep 1/3	Arbitrary
+	Medium 1/3	$\geq 2\text{cm}$
+	Shallow 1/3	$\geq 5\text{cm}$
-	Medium or deep 1/3	$\geq 4\text{cm}$

LVSI: Lymphovascular space invasion

3.7 Recording of follow-up data:

3.7.1 Preoperative assessment:

a) Standard preoperative laboratory tests determined by each center: (e.g., routine blood and urine test, coagulation function, blood liver, kidney function, electrolytes, HIV, RPR,

hepatitis markers)

- b) 12-lead ECG
- c) Tumor indicators: SCC antigen test (SCCA) and CA-125
- d) HPV typing test and TCT test in the last 3 months (only one preoperative test is required)
- e) Pathology or pathology consultation at each center (LEEP or conization is required for IA1 with LVSI and IA2).
- f) Imaging (CT scan of the chest, enhanced CT of the upper abdomen and pelvis, enhanced MRI to assess lesion size or PET-CT to assess retroperitoneal lymph node metastases)
- g) Collection of relevant medical history, height and weight, demographic data, and health insurance-related information of the patients
- h) Record all medications (including prescription drugs, over-the-counter drugs, vaccination, antibiotics, herbal medicine) used by the patient in the past 3 months
- i) Sign the informed consent form
- j) Record an inclusion criteria screening form
- k) Complete the randomization procedure, entering randomization codes for patients and recording the results
- l) Sign the informed consent form for the relevant surgery
- m) Patients may scan the QR code to register for the web-based follow-up platform

[Note]:

- **Pathologic evaluation:** Each patient must have a clear histologic diagnosis of cervical squamous cell carcinoma, cervical adenocarcinoma, or cervical adenosquamous carcinoma prior to radical cervical cancer surgery. If the cervical lesion is relatively evident, although the biopsy pathology shows patches of squamous cells without clear interstitial infiltration, the clinical presentation of the lesion is consistent with invasive cervical cancer, and then the patient may still be included in the study.
- **Clinical assessment:** cervical lesion size was measured by pelvic-enhanced MRI; the presence of metastases in the parametrium was determined by physical examination of the operator; and lymph node status was assessed by pelvic-enhanced MRI in combination with other imaging such as PET-CT.

3.7.2 Documentation of the surgical procedure

- a) Surgery based on randomized outcome: open or laparoscopic operation.
- b) Record intraoperative and postoperative information (including details of the procedure, duration of surgery, duration of anesthesia, intraoperative bleeding, intraoperative complications, details of blood transfusion and any other special circumstances surrounding the procedure).

3.7.3 Post-treatment follow-up records

One week after the end of treatment.

- a) Record postoperative pathology results and corresponding follow-up treatment plan
- b) Review laboratory tests (e.g. blood and urine routine test, coagulation function, blood liver, kidney function, electrolytes, drainage fluid creatinine)
- c) Postoperative indwelling catheter for 3-6 weeks and review of residual urine when the catheter is removed
- d) Postoperative complications (lymphatic cysts, dysuria, vaginal bleeding)

Review every 3 months for 2 years after completion of treatment with:

- a) Imaging examinations (chest CT + pelvic enhancement MRI + upper abdomen enhancement MRI or PET-CT)
- b) Tumor indicators: SCC antigen test (SCCA) and CA-125
- c) HPV and TCT test (once a year after completion of treatment)
- d) Adverse events recording
- e) Assessment of quality of survival and quality of sexual life using the Quality of Survival Scale for Cancer Patients (EORTC QLQ-C30 v3.0), the Cervical Cancer Sexual Life Scale (EORTC QLQ-CX24), and the Patient Reported Clinical Outcome Assessment Scale for Cervical Cancer PRO147 (V1.0).

After 2 years, the study will be reviewed every 6 months until the end of the trial. The review will include gynecological examination, tumor indicators (SCC antigen detection (SCCA) and CA-125), TCT examination and HPV examination, imaging (chest CT + pelvic enhancement MRI + upper abdomen enhancement MRI or PET-CT), and adverse event records.

3.8 Criteria for Patient Withdrawal

Patients have the right to withdraw from the trial treatment or study at any time without any reason. The investigator also has the right to withdraw a patient from the trial treatment or study in the event of secondary disease, adverse events, protocol violations, administrative reasons, or other reasons. Participation in the study, whether or not the affected patient participates, will not affect the relationship between the patient and the physician and will not result in a loss of medical or other benefits to the patient. However, in such cases, the investigator will make appropriate efforts to determine and document the reasons for the patient's voluntary withdrawal from the study. If a patient withdraws from the study, a complete final evaluation should be conducted at the time of patient withdrawal. This will be reported along with the study results and all attempts to locate patients lost to follow-up will also be documented.

Patients will be seen by their physician if they withdraw from the study. According to routine gynecologic oncology protocols, they should continue to receive care and treatment from an experienced physician until further follow-up is deemed unnecessary

by the treating physician.

Patients will be withdrawn from the study under the following circumstances:

- 1) Study completion/termination, or death
- 2) Patient demands withdrawal
- 3) Patient is unable or unwilling to cooperate with follow-up
- 4) Patient has other serious, non-surgical complications
- 5) Patient's follow-up information cannot be obtained
- 6) The study is terminated or cancelled at the request of the sponsor
- 7) Other relevant reasons

If a patient moves to another treatment center and requires changing of physician, the investigator will make a reasonable attempt to locate that center's physician and request cooperation in order to complete the follow-up.

In many cases, patient withdrawal from the study constitutes discontinuation of treatment and/or discontinuation of completion of related forms, such as quality of life. In these cases, the investigator should obtain the patient's permission to continue monitoring their disease status (relapse, survival, toxicity, etc.) through the patient's record.

Excessive exit rates can make a study uninterpretable, and therefore, unnecessary subject dropouts should be avoided.

3.9 Combination and simultaneous treatment:

[figure not shown]
Supplementary therapy will be administered according to the postoperative pathological findings of the patients. Those with high-risk factors who have positive parametrium will be supplemented with external pelvic irradiation therapy + cisplatin/carboplatin concurrent chemotherapy, those with positive vaginal margins will be selected for external pelvic irradiation therapy + retrovaginal radiotherapy + cisplatin/carboplatin concurrent chemotherapy, and those with positive pelvic lymph nodes will be treated with 1 course of systemic chemotherapy + external pelvic irradiation radiotherapy ± extended field radiotherapy adjacent to the abdominal aorta + cisplatin concurrent chemotherapy + 3-6 courses of adjuvant systemic chemotherapy after radiotherapy. Those with intermediate risk factors will be treated with external pelvic irradiation radiotherapy + cisplatin concurrent chemotherapy, and those with positive proximal margins will be treated with external pelvic irradiation radiotherapy EBRT + cisplatin concurrent chemotherapy + retrovaginal radiotherapy. Targeted immunotherapeutic agents such as bevacizumab and PD-1, which have just obtained some results in clinical studies, are not considered in this trial for the time being. It could be used according doctor's orders.

3.10 Outcome measurements:

- 1) Main outcome indicators: 5-year OS.
- 2) Secondary outcome measurements: 5-year PFS, refer to RECIST criteria.
- 3) Other outcome measurements: operation time, anesthesia time, intraoperative bleeding volume, intraoperative complications, postoperative complications, postoperative pain score, postoperative hospital stay, one-month postoperative survival quality, one-year postoperative survival quality, sexual quality of life.
- 4) Other evaluation parameters: patient's demographic characteristics, signs and symptoms, stage, pathological type, tumor site, comorbidities, medical history, length of hospital stay and cost.
- 5) This study intends to sample and collect intraoperative tumor tissues from tumor patients and evaluate specific tumor stages with genetic testing to guide later treatments such as targeted or immune therapies. Histological studies and molecular studies will also be conducted.

	Pre-phase	0-12 months	12-24 months	24-36 months	36-60 months
Meet the researchers	X				
Obtain IRB approval	X				
Funding application	X				
Enrollment of study patients		X	X	X	
Data monitoring		X	X	X	X
Data collection		X	X	X	X
Data analysis					X
Summary and discussion					X

3.11 Subjective schedule

Note: For patients with stage IB1, IB2, IIA1, IB3, and IIA2, the surgical method will be selected according to the maximum diameter of the mass. C1 type hysterectomy will be used for diameters <2 cm, C2 type hysterectomy will be used for diameters >4 cm, and C1 type or C2 type hysterectomy will be selected by the surgical team members according to the actual intraoperative condition for diameters between 2 cm and 4 cm.

3.12 Sample size

This study uses a non-inferiority trial design, and the primary outcome is the rate of OS at 5 years. The sample size is calculated based on the difference between the two groups of 5-year OS rate. The 5-year OS rate of the patients in the open surgery group is estimated to be 72% based on the previous clinical data from our hospital.

Based on the assumptions of (i) the 5-year OS rate of 72% in the open surgery group, (ii) a non-inferiority margin of 8%, (iii) 80% power, and (iv) a one-sided alpha of 0.025, the sample size estimation resulted in 495 subjects per group (calculated with SAS software, version 9.4). Considering a 10% drop-out rate and the randomization scheme with block size of 6, a total of 1104 subjects should be randomized (552 per group).

3.13 Recruitment methods:

The study team centers will advertise this study at their cervical cancer clinic. If the patients are interested, they will be further introduced in detail about the study background, randomization and surgical procedures, and the patients can voluntarily choose whether to participate in the trial. After patients sign the informed consent forms, members of the study team will review their eligibility according to the inclusion and exclusion criteria. Patients will then be randomized to receive either of the surgical

procedures. Finally, the patients will be followed up according to the follow-up schedule.

IV. Allocation, Blinding and Unblinding

4.1 Allocation of the interventions

4.1.1 Allocation sequence generation: In this study, a centralized block randomization with a block size of 6 will be used to randomly assign patients to the laparoscopic surgery group or the open surgery group at a 1:1 ratio. The randomization scheme will be completed by an independent statistical team at the Clinical Trial Center of the Children's Hospital of Fudan University by creating and sequencing random seed numbers (SAS 9.4 software). The intervention protocols determined by the random assignment sequence will be in sequentially numbered, non-transparent, sealed envelopes by zone: each of the 6 subgroups for each zone will be placed sequentially in six small, non-transparent, sealed envelopes numbered from 1 to 6, and then uniformly placed in the same large envelope marked with the corresponding zone number. The randomization assignment will be administered by the central coordinator at the Obstetrics and Gynecology Hospital of Fudan University who is not involved in the implementation of the intervention or the outcome observation. The enrollment is competitive, and the sub-center coordinator will contact the central coordinator before the inclusion of the first patient in each group. The central coordinator will follow the randomization scheme and assign the large envelopes with the group numbers to each center following the order of contact. Each sub-center will open the envelopes according to the order of signing the informed consent form, and strictly follow the numbered order of the envelopes, and then inform the participating physicians of the assignment scheme and complete written registration form.

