4.1.2 Allocation concealment mechanism

- 1) In this study, the surgical procedures will be selected in a randomized manner, and the CTU members will place the intervention modality in an envelope and give it to each center's coordinator who is not involved in the implementation of the intervention or the observation of the outcome to manage the allocation. The envelope will be opened by the investigators at each center following the enrollment order, to realize blinded preoperative randomization.
- 2) Data will be entered by dedicated study staff, who will be blinded to the randomization allocation and surgical procedure.

4.1.3 Assignment implementation (who generates the serial numbers, who recruits the subjects, and who assigns them)

- 1) The surgeons will perform the recruitment and obtain informed consent, and perform the surgical procedure.
- 2) The CTU team designs the randomization method and generates the corresponding

envelopes.

- 3) The allocation of surgeries according to the order of informed consent signed by the study participants in each center according to the randomization method to achieve an equal distribution of reporters in the open and lumpectomy groups.
- 4) The randomization staff will record the randomization numbers and procedure.
- 5) Follow-up of each patient and recording of relevant data and adverse events will be performed by dedicated follow-up personnel.
- 6) Data entry into the RedCap database will be performed by dedicated data entry personnel.
- 7) The CTU and the principal investigator will perform statistical analyses.

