4.2 Blinding

4.2.1 Who to blind and how to implement it

- 1) The specific procedure will not be known to the surgical team of each center until after the patients have been randomized during the administration phase of the intervention.
- 2) The randomization process will not be known to data entry personnel after the operation.
- 3) Statisticians will also be unaware of the randomization process.
- 4) The randomization process is also unknown to the personnel responsible for endpoint evaluation.

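### A single printed block size of 6, sent whole to one centre, lets recruiting surgeons deduce some upcoming arms: at most 25% of assignments with certainty, fewer with partial knowledge

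*Combined protocol and SAP*

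**What the plan says.** Section 4.1.1 (Allocation sequence generation) specifies that "a centralized block randomization with a block size of 6 will be used to randomly assign patients to the laparoscopic surgery group", with open surgery as the other arm in a 1:1 ratio. Section 3.12 repeats the block size when it rounds the sample size, and Section 11.1 says that the protocol has gone to every sub-center.

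The blocks are physical packs: six opaque, sealed envelopes numbered 1 to 6 inside one large envelope. On supply, the text reads "The enrollment is competitive, and the sub-center coordinator will contact the central coordinator before the inclusion of the first patient in each group". Packs are then issued centrally, and whoever holds that central role is to "assign the large envelopes with the group numbers to each center following the order of contact". I read zone and group here as meaning block. That is an inference, but the six numbered envelopes support it.

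Each centre opens its envelopes in consent order "and then inform the participating physicians of the assignment scheme", and keeps a written register. On roles, Section 4.1.3 says "The surgeons will perform the recruitment and obtain informed consent, and perform the surgical procedure". Section 3.13 adds that, after consent and before randomization, "members of the study team will review their eligibility according to the inclusion and exclusion criteria".

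The stated protection, besides the opaque envelopes and coordinators who take no part in treatment or outcome assessment, is in Section 4.2.1: "The specific procedure will not be known to the surgical team of each center until after the patients have been randomized".

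**The concern.** With one known block size, the early assignments in a block constrain the later ones. Once three of one arm have been opened, everything left in that pack is the other arm. The surgical approach cannot be hidden from the surgeon, and the same people decide whom to approach. The safeguards cover the unopened envelope; none addresses inference from opened ones.

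Foreknowledge matters before consent, when an approach can be delayed or discouraged. After consent the order is fixed, and the remaining route is the eligibility review. Many entry criteria are objective, but inclusion h (compliance with follow-up) and exclusion a (contraindication to surgery) call for judgement.

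The analysis would not repair selection at entry. Intention-to-treat keeps patients in their assigned arm but does not undo who was entered. The adjusted model in Section 5.3.2 c uses blood loss, operative duration and postoperative pain, which all arise during or after surgery, so it does not correct a baseline imbalance.

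**Working it through.** **Inputs.** Block of 6 at 1:1 (4.1.1, 3.12); 5-year OS 72%, margin 8 points, 80% power, one-sided alpha 0.025, 10% drop-out, 1104 patients (3.12); enrolment April 2021 to April 2024, 36 months (2.1). The documents give no predictability figure, no number of surgeons per centre, and no statement of how widely opened assignments are shared.

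**The plan's own figure.** n per group = (1.960 + 0.842)² × 2 × 0.72 × 0.28 / 0.08² = 494.5, so 495. Then 495/0.9 = 550 per group, 1100 in all; 1100/6 = 183.3, rounded up to 184 blocks; 184 × 6 = 1104. Reproduced.

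**Full knowledge of the block.** There are C(6,3) = 20 equally likely orders. An arm is certain when all three of the other arm have been used. The best guess is the arm used less often so far.

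| Position | 1 | 2 | 3 | 4 | 5 | 6 | Sum |
|---|---|---|---|---|---|---|---|
| P(arm certain) | 0 | 0 | 0 | 0.1 | 0.4 | 1.0 | 1.5 |
| P(best guess correct) | 0.5 | 0.6 | 0.6 | 0.7 | 0.7 | 1.0 | 4.1 |

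- Certain: 1.5/6 = 25.0%; 184 × 1.5 = 276 of 1104.
- Best guess: 4.1/6 = 68.3%, against 50% by chance.
- Certain assignments per block: one in 12 of the 20 orders, two in 6, three in 2.

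**Partial knowledge.** Suppose each earlier case is known independently with probability f (assumed) and the position in the block is known. Certainty needs all three used-up cases of one arm to be known, so the share is 25% × f³.

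| f (assumed) | Certain | Best guess |
|---|---|---|
| 1/3 | 0.9% | 56.1% |
| 1/2 | 3.1% | 58.4% |
| 2/3 | 7.4% | 61.0% |
| 1 | 25.0% | 68.3% |

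If the position is hidden as well, simulation at f = 1/3, 1/2 and 2/3 gives 0.0% certain and guess accuracy of about 55%, 57% and 60%.

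**Varied block sizes 4, 6 and 8, equally likely, sizes undisclosed, whole centre sequence known.**
- Block starts visible: an arm is certain only once four of the other arm have been seen, which happens only in blocks of 8. There, on average 20% × 8 = 1.6 assignments are certain. Per three blocks this is 1.6/(4 + 6 + 8) = 8.9%.
- Block starts hidden (simulation, two runs of 75,000): 2.2% to 2.3% certain, 68.0% to 68.1% best guess.

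**Pooled list, released singly, recruiter knows only own-centre cases.** For a centre with one sixth of enrolment (assumed) and list position known: 25% × (1/6)³ = 0.1% certain, 53.4% best guess. For a one-half share (assumed): 3.1% and 58.4% if position is known, or 0.0% and about 57.4% if it is hidden. The price is arm balance within the centre: the SD of the arm difference is √(1104 × 1/6 × 5/6) = 12.4 for a centre of 184. Whole blocks of 6 allow a difference of at most 3.

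**Workload.** One contact per block: 184/36 = 5.1 a month. One per patient: 1104/36 = 30.7 a month.

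**The case against.** The strongest reply is that 25% needs a recruiter who knows every earlier case in the pack. The plan says that participating physicians are informed; it does not say that each recruiter learns every colleague's assignments. Section 2.3 speaks of surgeons in the plural without a number per centre. Section 4.1.2 places a coordinator uninvolved in treatment between the envelopes and the surgeons, though the same item has investigators opening them, so whether a recruiter sees the envelope number is unstated. This stands: 25% is an upper bound, and a reader who takes it as the expected level goes beyond the text. Nor should 0.9% to 7.4% be taken as the range for partial knowledge, because it depends on the assumed f and on a known position.

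A second reply is that varied block sizes do little for guessing. That also stands for someone who sees the whole centre sequence: accuracy stays near 68%. A reader might infer that a pooled list is therefore required. The documents do not support that. Section 4.1.3 item 3 appears to seek an equal split between arms within each centre, which whole blocks deliver and a pooled list loosens. In a surgical trial that is a fair trade-off to dispute.

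A reader might also see a contradiction in who hands out envelopes, since Section 4.1.2 says "the CTU members will place the intervention modality in an envelope and give it to each" centre's coordinator while 4.1.1 gives distribution to the central coordinator. Preparation by the CTU, central distribution and local handling can be read as one chain. Likewise, Section 4.2.2 keeps the randomization form with dedicated staff at each centre. It does not say that the form lists future assignments, so no leak can be inferred from it.

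**Conclusion.** The concern holds as a risk. One fixed, printed block size, packs visible as blocks at a single centre, and recruiters who operate and learn opened assignments together make some upcoming arms deducible before a patient is approached or screened. The ceiling is 25% certain (276 of 1104) with 68.3% best-guess accuracy. The actual level lies between 0% and 25% certain and depends on facts that the documents do not give. The calculation rests on reading zone and group as block, and on the assumed f for any intermediate value.

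A reader might go on to infer that the survival comparison will be biased, or in which direction. The documents do not support either step: they do not show that anyone would act on a guess, consent order limits what can be done after consent, and many entry criteria are objective. This is an improvement that should be made at modest cost, not a flaw that invalidates the design.

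**What to change.** For blocks not yet issued:

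1. Generate new lists with randomly varied block sizes, for example 4, 6 and 8. Keep the sizes in a document held by the CTU and out of anything sent to sites.
2. Stop shipping packs of six. Have the existing central coordinator release one assignment at a time, after consent and eligibility are recorded, using a code that does not show where a block starts.
3. Keep the lists within centre. Balance in each centre is preserved (difference at most 8/2 = 4 instead of 3), and certain assignments fall from at most 25% to about 2%, or about 9% if block starts remain visible. Guess accuracy stays near 68% for someone who knows the whole centre sequence.

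It would also help to state one hand-over route in 4.1.1 and 4.1.2, and to say in 4.2.2 that any form held at a centre records past assignments only.

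Release from a pooled list is an option for the sponsor to weigh. It lowers guessing further, least at a centre with a large share of enrolment, at the price of the looser within-centre balance shown above.

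Cost: one coordinator contact per patient (about 31 a month instead of 5) and new lists. The sample size is unaffected apart from rounding to whole blocks. The change does nothing for blocks already used; for those, baseline characteristics could be compared by arm and position in the block, as description only.
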